3.2. Planned Number of Patients and Countries

Approximately 340 patients (approximately 170 patients per treatment group) are planned to be enrolled in this study to have approximately 288 completers (144 completers per treatment group). A 15% drop-out rate is anticipated.

Details on definition of evaluable patients and sample size are given in Section 9.

The study is planned to be conducted in approximately 13 countries in approximately 65 investigational centers. The study is expected to start in approximately September 2019 and last until approximately August 2021.

3.3. Justification for Study Design and Selection of Population

The study population will be composed of female and male patients, aged 18 to 70 years, inclusive, with a diagnosis of migraine and MDD. Patients must have been diagnosed with migraine (as defined by the ICHD-3 criteria [IHS, 2013], see Appendix I) at least 12 months prior to the screening visit (V1). The diagnosis of migraine will be prospectively confirmed via a review of migraine data recorded daily during a 28-day baseline period in an electronic diary device. Patients must also have a history of MDD according to the DSM-V criteria at least 12 months prior to the screening visit (V1) and have active symptoms of depression as assessed

by a PHQ-9 score of at least 10 at the screening visit (V1). Investigators must document that patients had the diagnosis of migraine and MDD for at least 12 months prior to the screening visit (V1). MDD is a common comorbidity with migraine. Post hoc analyses of the HALO CM study indicated that depressive symptoms improved in migraine patients with baseline PHQ-9 of 10 to 19. This study is designed to further evaluate the efficacy of fremanezumab in this population.

Commercially approved dosing regimens will be investigated in the double-blind treatment phase. Both the monthly dose of 225 mg and quarterly dose of 675 mg, which will be used in the current study in the double-blind and the open-label periods, respectively, were equally efficacious in the pivotal trials. For treatment details, see Section 5.1.

One objective of this study is to determine whether migraine and depression are affected independently by fremanezumab or whether improvement in one disease precedes and may causally improve the other disease via their bidirectional association (see Section 1.1.2 for further background information). By assessing both migraine and depression symptoms at multiple time points and by having placebo patients cross over to active treatment, we will have more data points by which to make this assessment. Additionally, the open-label extension phase is intended to provide the placebo-treated patients the opportunity to receive potential benefit from therapeutic doses. It also provides an opportunity to further explore efficacy and tolerability in this patient population and to generate data on switching from the monthly to the quarterly dose.

To provide additional expertise in depression, anxiety, and suicidality assessments and management, psychiatrists will be included in the study team at the investigational site.

A randomized, double-blind, parallel-group, placebo-controlled design is appropriate given the objectives of this study. Furthermore, this design is consistent with the recommendations of the Classifications Committee of the IHS for controlled trials of preventive drugs in migraine ([Tfelt-Hansen, 2012](#)).

3.4. Stopping Rules for the Study

There are no formal rules for early termination of this study. During the conduct of the study, serious adverse events will be reviewed (Section 7.1.5) as they are reported from the investigational centers to identify safety concerns.

The study may be terminated by the sponsor for any reason at any time. For example, the sponsor should terminate the study in the event of:

- new toxicological or pharmacological findings or safety issues invalidate the earlier positive benefit-risk assessment

A patient may discontinue participation in the study at any time for any reason (eg, lack of efficacy, consent withdrawn, or adverse event). The investigator and/or sponsor can withdraw a patient from the study at any time for any reason (eg, important protocol deviations as defined in [Appendix C](#), noncompliance, or adverse event). In addition, patients with positive suicidality findings or abnormal hepatic laboratory values (eg, alanine aminotransferase [ALT], aspartate aminotransferase [AST], alkaline phosphatase [ALP], gamma glutamyl transpeptidase, bilirubin

[total, direct, or indirect], or international normalized ratio) may meet the criteria for discontinuation from the IMP (Section 7.1.1 and Section 7.1.5.1).

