4.3. Withdrawal Criteria and Procedures for the Patient

Each patient is free to withdraw from the study or discontinue from IMP at any time, without prejudice to their continued care. Patients must be withdrawn from the IMP if any of the following events occur:

1. Patient withdraws consent or requests discontinuation from the IMP or withdrawal from the study for any reason.
2. Patient develops an illness that would interfere with his/her continued participation.
3. Patient is noncompliant with the study procedures and assessments or administration of IMPs in the opinion of the investigator.
4. Patient takes prohibited concomitant medications or receives prohibited therapies as defined in this protocol.
5. A female patient has a confirmation of pregnancy during the study from a positive urine pregnancy test.
6. The sponsor requests withdrawal of the patient.
7. Patient experiences an adverse event or other medical condition that indicates to the investigator that continued participation is not in the best interest of the patient.

Patients should be treated with standard of care after withdrawal from or termination of the study as appropriate.

Investigators should attempt to obtain information on patients in the case of withdrawal from the study or discontinuation from IMP. Results of any evaluations and observations, together with a narrative describing the reason(s) for withdrawal from the study or discontinuation from IMP, must be recorded in the source documents. The electronic case report form (eCRF) must document the primary reason for withdrawal from the study or discontinuation from IMP.

See [Appendix F](#) for information regarding how the study will define and address lost to follow-up patients to help limit the amount and impact of missing data.

If the reason for withdrawal from the study or discontinuation from IMP is an adverse event and/or clinically significant abnormal laboratory test result, monitoring will be continued as applicable (eg, until the event has resolved or stabilized, until the patient is referred to the care of a health care professional, or until a determination of a cause unrelated to the IMP or study procedure is made). The specific event or test result (including repeated test results, as applicable) must be recorded on both the source documentation and the eCRF; both the adverse events page and the relevant page of the eCRF will be completed at that time.

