5.8. Procedures for Monitoring Patient Compliance

The investigator will be responsible for monitoring patient compliance until completion of the IMP administration according to the protocol or discontinuation from IMP. If the investigator or the sponsor determines that the patient is not in compliance with the study protocol, the investigator and the sponsor should determine whether the patient should be withdrawn from the study. The Independent Ethics Committee/Institutional Review Board (IEC/IRB) should be notified.

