9.2. Analysis Sets

9.2.1. Intent-to-Treat Analysis Set

The intent-to-treat (ITT) analysis set will include all randomized patients.

In the ITT analysis set, treatment will be assigned based on the treatment to which patients were randomized, regardless of which treatment they actually received.

Data collected from patients after treatment discontinuation will be included in the ITT analysis set.

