APPENDIX C. QUALITY CONTROL AND QUALITY ASSURANCE

Protocol Amendments and Protocol Deviations

Protocol Amendments

No changes from the final approved (signed) protocol will be initiated without the prior written approval or favorable opinion of a written amendment by the Independent Ethics Committee/Institutional Review Board (IEC/IRB) and national and local competent authorities, as applicable, except when necessary to address immediate safety concerns to the patients or when the change involves only nonsubstantial logistics or administration. The principal investigator at each investigational center, the coordinating investigator (if applicable), and the sponsor will sign the protocol amendment.

Important Protocol Deviations

Any deviation from the protocol that affects, to a significant degree, (a) the safety, physical, or mental integrity of the patients in the study and/or (b) the scientific value of the study will be considered an important protocol deviation. Important protocol deviations may include non-adherence on the part of the patient, the investigator, or the sponsor to protocol-specific inclusion and exclusion criteria, primary objective variable criteria, or Good Clinical Practice (GCP) guidelines; noncompliance to IMP administration; and use of prohibited medications. Important protocol deviations will be identified and recorded by investigational center personnel on the electronic case report form (eCRF). All important protocol deviations will be reported to the responsible IEC/IRB, as required.

When an important protocol deviation is reported, the sponsor will determine whether to withdraw the patient from the study or permit the patient to continue in the study, with documented approval from the medical expert. The decision will be based on ensuring the safety of the patient and preserving the integrity of the study.

Changes in the inclusion and exclusion criteria of the protocol are not prospectively granted by the sponsor. If investigational center personnel learn that a patient who did not meet the protocol inclusion and exclusion criteria was entered in a study, they must immediately inform the sponsor of the important protocol deviation. If such patient has already completed the study or has withdrawn early, no action will be taken but the deviation will be recorded.

Information to Study Personnel

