#### **3.1.4. Per-Protocol Analysis Set**

The PP analysis set is a subset of the mITT analysis set including only patients without important protocol deviations during the double-blind treatment period, including any deviation of the inclusion/exclusion criteria or any deviations or omissions of the IMP administration. Patients with less than 75% diary compliance during the double-blind treatment period will be excluded from the PP analysis set. A blinded data review meeting will be conducted prior to the database lock in order to determine the exclusion of the patients from the PP analysis set. After database lock and unblinding, patients who received study drug different from the study drug they were randomized to will also be excluded from the PP analysis set.

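### Sections 3.4, 5.8 and Appendix C allow removal from the study, not only from study drug, for deviations or noncompliance, which cuts outcome follow-up short without need

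*Protocol*

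**What the plan says.** Three places in the protocol treat leaving the study as an available response to a deviation or to poor compliance.

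- Section 3.4: "The investigator and/or sponsor can withdraw a patient from the study at any time for any reason (eg, important protocol deviations as defined in". The sentence goes on to cite Appendix C and gives noncompliance and adverse events as further examples.
- Section 5.8, when a patient is judged not to be complying: "the investigator and the sponsor should determine whether the patient should be withdrawn from the study".
- Appendix C, when an important deviation is reported: "the sponsor will determine whether to withdraw the patient from the study or permit the patient to continue in the study". Stopping drug while remaining in follow-up is not named as an option.

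Section 4.3 is framed around study drug. Its list opens: "Patients must be withdrawn from the IMP if any of the following events occur". Item 3 is "Patient is noncompliant with the study procedures and assessments or administration of IMPs in the opinion of the investigator". Item 6 is looser: "The sponsor requests withdrawal of the patient".

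On analysis, Protocol 9.2.1 states: "Data collected from patients after treatment discontinuation will be included in the ITT analysis set". SAP 3.1.4 takes patients with important deviations out of the per-protocol (PP) set and adds: "Patients with less than 75% diary compliance during the double-blind treatment period will be excluded from the PP analysis set".

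**The concern.** Stopping study drug and leaving the study are different events. Only the second ends outcome collection. Removal for a deviation or for noncompliance is decided after randomization, at someone's discretion, and may be related to how the patient is doing. The outcomes lost are ones the existing visit schedule would otherwise have captured, and they cannot be recovered later.

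The endpoints exposed are the 12-week migraine-day average, the week-8 HAM-D 17 (the key secondary endpoint), the 50% responder endpoint and the week-12 scales. The route is not remote: Section 6.1.1 asks for about 75% diary compliance after randomization and has sites monitor it, and Appendix C counts non-adherence by the investigator or sponsor as a possible important deviation.

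**Working it through.** **1. What each section does to participation.** Sections 3.4, 5.8 and Appendix C concern the study. The Section 4.3 list concerns study drug, and noncompliance is on it. No section sets a diary and visit schedule for a patient who stops drug and stays in. Section 9.2.1 has a use for data after drug is stopped, but a patient removed from the study supplies none.

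**2. What happens to a removed patient's data.**

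- Visits: Section 3.1 gives one final visit with the visit 6 procedures. SAP 4.4 leaves early-termination data out of by-visit summaries.
- Diary: entries end at that visit (Table 4 notes).
- Analysis sets: the patient stays in ITT (all randomized), and in mITT if dosed and with at least 10 days of post-randomization assessment (SAP 3.1.2).
- Primary value, SAP 6.1 formula (1): migraine days ÷ diary days × 28. The 12-week period has 3 × 28 = 84 days. Removal after 28 full diary days lets 28/84 = 33% of the period stand for all of it. At the 10-day minimum it is 10/84 = 12%.
- HAM-D 17: removal before day 57 leaves week 8 missing. The MMRM still uses a week-4 score if there is one.
- Responder endpoint: SAP 6.3.2.1 sets early discontinuation from the study to non-response.
- Multiple imputation (SAP 6.2.3.2): only fremanezumab patients who stop for adverse event or lack of efficacy are moved to the placebo group. Other removals are imputed from their own arm.
- Intercurrent events: SAP 1.3 lists lack of efficacy, adverse event, prohibited therapy and COVID-19. Prohibited medication is also an important deviation in Appendix C, so that class is covered. Eligibility deviations, dosing deviations and noncompliance are not.

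**3. The plan's own figures reproduce.** Inputs from Section 9.1: differences of 2 days (SD 5.2) and 2 points (SD 6), two-sided 0.05, 144 per group, 15% drop-out. Formula: n per group = 2(z₁₋α/₂ + z₁₋β)²σ²/δ².

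- Primary: 2 × (1.960 + 1.282)² × 5.2² / 2² = 142.1, so 143 (144 stated). Noncentral-t power at 144 is 90.2%.
- HAM-D 17: 2 × (1.960 + 0.842)² × 6² / 2² = 141.3, so 142. Noncentral-t power at 144 is 80.5%.
- Randomized: 288 / 0.85 = 338.8, so 339 (about 340 stated).

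The sample size is not in question.

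**4. What can be said about size.** Expected drop-outs: 340 × 0.15 = 51. The share due to deviation or noncompliance is not given. As an assumption, take 10% to 50%: k = 5.1 to 25.5 patients. If all were kept and gave a week-8 HAM-D 17, n per group = 144 + k/2 = 146.6 to 156.8, and HAM-D 17 power would be 81.2% to 83.7% against 80.5%. This overstates the gain. Removals after day 57 cost no week-8 score, the MMRM already uses earlier scores, and noncompliant patients may supply little.

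For bias in the primary contrast, let p be the share of an arm removed and d the mean gap between the prorated value and the one full follow-up would have given. The shift is p_F·d_F − p_P·d_P. It is zero when p and d are equal across arms. The documents give neither quantity, so neither sign nor size can be stated.

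**The case against.** The case on the other side has real weight, and it rules out several stronger readings.

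- A reader might infer that removed patients drop out of ITT and mITT, so that the PP repeat loses the same people. They do not. Membership is as set out above; what is lost is later observation.
- A reader might infer that Section 4.3 confines noncompliance to stopping drug and so flatly contradicts 3.4. It does not go that far. It is silent on whether such a patient stays in the study, item 1 mentions study withdrawal, item 6 speaks of withdrawing the patient, and later text handles the two events together.
- A reader might infer that the SAP has no handling for these patients. It has proration, MMRM, multiple imputation on the ITT set and the non-response rule.
- A reader might add the retained patients to the evaluable number and claim higher primary power. That fails, because patients with at least 10 diary days are already analysed.
- A reader might infer a one-directional bias. Sponsor and investigators are blinded in this phase, which limits removal that depends on arm, and nothing in the documents points to a direction.

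Section 3.4 is also permissive. Appendix C offers continuation as the alternative, requires documented medical-expert approval, and bases the decision on patient safety and study integrity. Section 9.2.1 covers data that are collected and does not itself promise collection; the SAP's ITT definition omits that sentence, efficacy is analysed on mITT, and the SAP prevails.

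All of this narrows the point. None of it gives a reason to stop observing a willing patient because of a deviation that the PP set already handles.

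**Conclusion.** The point holds as a cheap improvement. The protocol permits discretionary study withdrawal for important deviations or noncompliance, and that truncates diary and HAM-D 17 follow-up for patients who could have stayed under observation. Except for prohibited therapy, the listed intercurrent events do not cover these removals.

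The effect is likely small and cannot be quantified from the documents, because the number affected is not given. The HAM-D 17 range of 81.2% to 83.7% rests on an assumed 10% to 50% share and complete retained data, so it is for scale only. No primary power gain and no direction of bias should be claimed.

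**What to change.** In Sections 3.4, 5.8 and Appendix C, remove protocol deviation and noncompliance, by themselves, as grounds for investigator or sponsor withdrawal from the study. State that these patients continue the diary and the already scheduled visit 3 to 5 assessments to day 85 unless they withdraw consent or cannot be reached. Their data are analysed as randomized, and the deviations are handled through the PP set.

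Reconcile this wording with three other places:

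- Section 4.3, including item 6;
- Section 9.7, under which patients who start prohibited therapies are discontinued from the study, whereas 4.3 lists prohibited medication and therapy under withdrawal from study drug;
- Section 5.10.2, under which a patient whose blind is broken is withdrawn from the study.

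No rule on when study drug is stopped needs to change, and none is proposed here.

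Cost: protocol wording in three places plus the reconciliation. Sites complete scheduled visits for a few more patients, some of whom will decline or supply limited data.

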3.5. Schedule of Study Procedures and Assessments

Study procedures and assessments with their time points are presented in [Table 4](#). Detailed descriptions of each method of procedures and assessments are provided in [Section 6](#) (efficacy assessments) and [Section 7](#) (safety assessments). Study procedures and assessments by visit are listed in [Appendix B](#). Investigators can contact patients in between study visits per their clinical judgment.

For Coronavirus disease 2019 (COVID-19) updates, see [Appendix P](#).

Table 4: Study Procedures and Assessments

Study period	Pretreatment (screening and baseline)	Double-blind treatment phase			Open-label extension phase	End of treatment/ Early termination ^{a/} Follow-up period
Visit number	V1	V2 ^b	V3	V4	V5 ^c	V6
Day and allowed time windows	Days -28 to -1	Day 1 +3 day(s)	Day 29 ±3 day(s)	Day 57 ±3 day(s)	Day 85 ±3 day(s)	Day 169 ±3 day(s)
Procedures and assessments	Screening	Randomization	Week 4	Week 8	Week 12	Week 24
Informed consent	X					
Inclusion and exclusion criteria	X	X				
Assign randomization/treatment number		X				
Medical and psychiatric history	X					
Record demographic characteristics	X					
Prior medication and treatment history ^d	X					
Physical examination, including height and weight ^e	X ^f	X	X	X	X	X
12-Lead ECG	X	X ^g	X ^g	X ^g	X ^g	X
Vital signs measurement ^h	X	X	X	X	X	X
Safety laboratory assessments	X	X	X	X	X	X
Serum β-HCG test ⁱ	X					
Urine β-HCG test ^{ij}		X	X	X	X	X
FSH ^k	X					
Inform patients of study restrictions and compliance requirements	X					
Review study compliance ^l		X	X	X	X	X
MMSE ^j	X					
PHQ-9 ^j	X		X	X	X	X
eC-SSRS ^{j,m}	X	X	X	X	X	X
HAM-D 17 ^{j,n}		X	X	X	X	X

Table 4: Study Procedures and Assessments (Continued)

Study period	Pretreatment (screening and baseline)	Double-blind treatment phase				Open-label extension phase	End of treatment/ Early termination ^a / Follow-up period
		V1	V2 ^b	V3	V4		
Day and allowed time windows	Days -28 to -1	Day 1 +3 day(s)	Day 29 ±3 day(s)	Day 57 ±3 day(s)	Day 85 ±3 day(s)	Day 169 ±3 day(s)	
Procedures and assessments	Screening	Randomization	Week 4	Week 8	Week 12	Week 24	
HAM-A ^{j,n}		X	X	X	X	X	
HIT-6 ^j		X	X	X	X	X	
CGI-S ^j		X	X	X	X	X	
MSQoL ^j		X	X	X	X	X	
WPAI:GH ^j		X	X	X	X	X	
Provide electronic headache diary ^o	X						
Complete electronic headache diary entries ^p	X	—————					X
Review electronic headache diary ^l		X	X	X	X		X
Return headache diary							X
Adverse events and health care resource utilization inquiry ^l	X ^q	X	X	X	X		X
Dispensing of IMP		X	X	X	X		
Administration of IMP ^f		X	X	X	X		
Hypersensitivity/ anaphylaxis ⁵		X	X	X	X		X
Concomitant medication and therapy inquiry ^l	X	X	X	X	X		X

^a In the case of early termination, site personnel should perform a follow-up phone call to ensure the patient does not report suicidal ideation or behavior. Phone calls should be performed once weekly for 2 weeks. If signs of suicidality are identified during the follow-up phone call, the site personnel should provide direction to the patient for further psychiatric evaluation at the site or at a community psychiatrist referenced by the site. Relevant emergency psychiatric care services should be notified in the event that the patient is deemed to be a threat to themselves.

^b Patients will complete the screening visit not more than 28 (+3) days before the randomization visit (V2 [day 1]). All visit 2 procedures must be performed before study drug administration.

^c Patients will continue into the open-label extension phase at week 12 and will all receive a quarterly dose of 675 mg sc fremanezumab.

- ^d Collection of prior medications for migraine and/or depression is limited to those medications administered within the past 10 years or for any indication with the past 5 months before screening (V1).
- ^e In addition, inquire and record start/stop date of menstrual period for women of child-bearing potential only at each visit as part of physical examination assessments.
- ^f Height will be measured only at the screening visit (V1).
- ^g This assessment will be done predose. A single ECG will be performed. If results are abnormal, the ECG will be repeated 1 time.
- ^h Before pulse and blood pressure are measured, the patient must be in a supine or semi-erect/seated position and resting for at least 5 minutes. The same position and arm should be used each time vital signs are measured for a given patient.
- ⁱ For details see [Appendix E](#).
- ^j On dosing days, the test or questionnaire should be completed before study drug administration.
- ^k The FSH assessment applies only to women thought to be postmenopausal at the screening visit (V1). If the results show an elevated FSH (>35 U/L) and the patient has had no menses for at least 12 months, they do not need urine pregnancy testing.
- ^l This is a required procedure for unscheduled visits. See further details in [Appendix B](#).
- ^m Patients will complete the eC-SSRS Lifetime version at V1 and will complete the eC-SSRS Since Last Visit version at all other visits. The eC-SSRS will be used in conjunction with a qualified clinician's clinical judgment to assess the patient's suicidal ideation (severity and intensity) and behavior.
- ⁿ A qualified staff member (ie, the investigator or a medically qualified person designated by the investigator) will perform this assessment.
- ^o Eligible patients will be given an electronic headache diary device and will be trained in its use and compliance requirements on the day of the screening visit (V1).
- ^p Patients will complete electronic headache diary entries about the previous day daily beginning on day -27 through the EOT/early withdrawal visit.
- ^q Inquiries about adverse events will be made before administering questionnaires on non-dosing days and before and after study drug administration on dosing days. Post-dose inquiries will be made before the patient leaves the study center.
- ^r Patients will be assessed for severe hypersensitivity/anaphylaxis reaction during and after administration of the IMP. Oxygen saturation and respiratory rate will be measured in cases of suspected anaphylaxis and severe hypersensitivity. See further details in [Appendix H](#).

β -HCG = beta-human chorionic gonadotropin; ECG = electrocardiography; eCRF = electronic case report form; CT = electroconvulsive therapy; eC-SSRS = electronic Columbia-Suicide Severity Rating Scale; EOT = end of treatment; FSH = follicle-stimulating hormone; HAM-A = Hamilton Anxiety Scale; HAM-D 17 = Hamilton Depression Rating Scale-17 items; HIT-6 = 6-item Headache Impact Test; IMP = investigational medicinal product; MMSE = Mini Mental State Examination; MSQoL = Migraine-Specific Quality of Life; PHQ-9 = Patient Health Questionnaire-9; WPAI:GH = Work Productivity and Activity Impairment Questionnaire General Health V2.0; V = visit.

